12.4 Interim / Preliminary Analysis

No preliminary analyses are planned.

12.5 Determination of Sample Size and Power Calculation

This is an exploratory study with no hypothesis-driven primary objectives. All available subjects who participated in and completed the MET54 study and received either MenACYW conjugate vaccine or Nimenrix® vaccine, as a part of the study, will be enrolled.

13 Ethical and Legal Issues and Investigator / Sponsor Responsibilities

13.1 Ethical Conduct of the Study / Good Clinical Practice

The conduct of this study will be consistent with the standards established by the Declaration of Helsinki and compliant with the ICH guidelines for GCP as well as with all local and / or national regulations and directives.

13.2 Source Data and Source Documents

"Source data" are the data contained in source documents. Source documents are original documents or certified copies, and include, but are not limited to, diary cards (booklets or ediaries), medical and hospital records, screening logs, informed consent / assent forms, telephone contact logs, and worksheets. The purpose of study source documents is to document the existence of subjects and to substantiate the integrity of the study data collected. Investigators must maintain source documents so that they are accurate, complete, legible, and up to date.

For missing or discrepant data on a diary card (booklet), the study coordinator will obtain verbal clarification from the subject, enter the response into the "investigator's comment" page of the diary card (booklet), and transfer the information to the CRB. For missing or discrepant data on a diary card (e-diary), the study site staff will obtain verbal clarification from the subject, enter the response in the source document, and transfer the information to the CRB.

The subject pre-screening log should list all individuals contacted by the Investigators to participate in the study, regardless of the outcome.

The Investigator must print^a any electronic records on an ongoing basis, sign and date them immediately after creation, and keep the printouts on file as source documents that can be verified by the Sponsor or an inspector against the electronic records. Any subsequent changes of an electronic record require the record to be re-printed, dated (with an indication of the date of change), and signed. Such records must also be kept together with the original printed copy.

_

Unless the electronic medical records are managed by validated computerized systems that are compliant with US 21 CFR Part 11, in which case they are acceptable on their own.

If an e-diary is used in this trial, the e-diary data, which has been integrated into the CRB, will be available on the vendor's web-based portal for review. At the end of the trial, data in the web-based portal will be stored and then will later be destroyed according to local regulation.

Good Documentation Practice should be followed by the Investigator and the site staff managing source documents.

13.3 Confidentiality of Data and Access to Subject Records

Prior to initiation of the study, the Investigator will sign a fully executed confidentiality agreement with Sanofi Pasteur.

Sanofi Pasteur personnel (or designates), the IECs / IRBs, and regulatory agencies, require direct access to all study records, and will treat these documents in a confidential manner.

In the event a subject's medical records are not at the investigational site, it is the responsibility of the investigator to obtain those records if needed.

13.4 Monitoring, Auditing, and Archiving

13.4.1 Monitoring

Before the start of the study (i.e., before the inclusion of the first subject in the first center), the Investigators and the Sponsor's staff or a representative will meet at the site-initiation visit to discuss the study protocol and the detailed study procedures. Emphasis will be placed on inclusion and exclusion criteria, visit timing, safety procedures, informed consent procedures, SAE reporting procedures, CRB completion, and the handling of samples and products. The Sponsor's staff or a representative will ensure and document that all material to be used during the study has been received at the site; and that the study investigator team and local Sponsor/delegate staff have been properly informed about the study, GCP and regulatory requirements, and the Sponsor's procedures. Specific training sessions for the study investigator team and the CRAs on these topics may be performed as necessary, and should be documented.

The following instruction manuals will be provided: the CRF Completion Instructions for entering data into the CRB, and the Operating Guidelines for detailed study procedures such as the product management and sample-handling procedures.

After the start of the study, the Sponsor's staff or a representative will be in regular contact with the investigational team through telephone calls and regular follow-up visits. The Investigator or delegate must be available for these visits, and must allow the Sponsor/delegate staff direct access to subject medical files and CRFs. During these visits, the Sponsor/delegate staff will:

- Evaluate the quality of the study progress (adherence to protocol and any study-specific guidelines, quality of data collection and document completion, signature of consent forms, occurrence of SAEs, sample and product management, cold-chain monitoring, archiving)
- Source-verify completed CRFs and any corresponding answered queries

- Determine the number of complete or ongoing issues identified at monitoring visits (e.g., protocol deviations, SAEs). Any identified problems will be discussed with the Investigator, and corrective or preventive actions will be determined, as appropriate.
- After all protocol procedures have been completed and the data have been entered into the CRB, the Investigator must still be available to answer any queries forwarded by the Sponsor. All data-related queries must be completed prior to database lock.

At the end of the study, a close-out visit will be performed to ensure that:

- The center has all the documents necessary for archiving
- All samples have been shipped to the appropriate laboratories
- All unused materials and products have been either destroyed or returned to the Sponsor

13.4.2 Audits and Inspections

A quality assurance audit may be performed at any time by the Sponsor's Clinical Quality Assessment department (CQA) or by independent auditors to verify that the study has been conducted according to the protocol, GCP and ICH requirements, and other applicable regulations. An inspection may be conducted by regulatory authorities. The Investigator must allow direct access to study documents during these inspections and audits.

13.4.3 Archiving

The Investigator must keep all study documents after the completion or discontinuation of the study, whatever the nature of the investigational center (private practice, hospital, or institution), for as long as required by applicable laws and regulations. In the absence of any applicable laws or regulations, study documents will be kept at a minimum for the duration indicated on the Clinical Trial Agreement (CTA). In no event, should study personnel destroy or permit the destruction of any study documents upon less than 90 days advance written notification to the Sponsor. In addition, study documents should continue to be stored, at Sponsor's sole expense, in the event that the Sponsor requests in writing that such storage continues for a period of time that exceeds that required by any applicable law or regulation or the CTA. The Investigator will inform Sanofi Pasteur of any address change or if they will no longer be able to house the study documents.

Archived data may be held on electronic records, provided that a back-up exists and that a hard copy can be obtained if required. The protocol, documentation, approvals, and all other documents related to the study will be kept by the Sponsor in the Trial Master File (TMF). Data on AEs are included in the TMF. All data and documents will be made available if requested by relevant authorities.

13.5 Financial Contract and Insurance Coverage

A CTA will be signed by all the parties involved in the study's performance, if relevant. The Sponsor has an insurance policy to cover any liabilities that may arise from use of the product and / or the study protocol.

13.6 Stipends for Participation

Subjects may be provided with a stipend according to local practice to compensate for the time and travel required for study visits and procedures.

## List of Abbreviations

AE adverse event

AESI adverse event of special interest

AR adverse reaction BL blood sample

CI confidence interval

CRF (electronic) case report form

CSR clinical study report

D day

DC diary card dil dilution

FAS full analysis set

FASP full analysis set for persistence FDA Food and Drug Administration

GM geometric mean

GMC geometric mean concentration

GMT geometric mean titer IU international unit

LLOQ lower limit of quantification

MD missing data

MedDRA Medical Dictionary for Regulatory Activities

PPAS per-protocol analysis set

PT preferred term

Q1; Q2; Q3 first quartile; second quartile (median); third quartile

RCDC reverse cumulative distribution curve

SAE serious adverse event
SafAS safety analysis set
SAP statistical analysis plan

SOC system organ class (primary)
TLF table(s), listing(s), and figure(s)
ULOQ upper limit of quantification

V visit

#### 1 Introduction

This study (MET62) will assess the immunogenicity and safety of a booster dose of the investigational quadrivalent Meningococcal Polysaccharide (serogroups A, C, Y, and W) Tetanus Toxoid Conjugate Vaccine (hereafter referred to as MenACYW conjugate vaccine) administered 3 years after a primary dose of MenACYW conjugate vaccine or Nimenrix® was administered to toddlers participating in the MET54 study. The persistence of the immune response against meningococcal serogroups A, C, Y, and W, 3 years after primary vaccination with either MenACYW conjugate vaccine or Nimenrix®, will also be described.

The epidemiology of Neisseria meningitidis (N meningitidis) can be described as complex, unpredictable, geographically variable, and changing over time. Meningococcal disease occurs worldwide in both endemic and epidemic forms with seasonal variation. In Europe, the incidence rate of Invasive meningococcal disease (IMD) has remained stable over the last 5 to 10 years, with the highest peak occurring in the population less than 4 years of age and a smaller peak in the 15 to 19 year old group. The highest incidence rate in Europe is caused by serogroup B, followed by C (1). The highest proportion of meningococcal cases was due to serogroup B in the population under 5 years of age. The highest proportion of serogroup C cases was observed in the population 25 to 44 years of age while the proportion of serogroup Y cases was highest in the population aged 65 years and above. Surveillance data from England and Wales showed an increase in endemic meningococcal serogroup W disease across all age groups, accounting for 15% of all IMD cases in 2013 - 2014 compared with an average of 1% to 2% of all IMD cases in earlier years (2). A gradual increase in serogroup Y IMD has also been recently reported in Sweden during 2005 – 2012 (3) (4). Nearly 50% of all IMD was caused by serogroup Y in 2012 (3). Similarly, an increase in the proportion of IMD caused by serogroup Y has been observed in other Scandinavian countries, accounting for 31% in Norway in 2009 – 2010 and 38% in Finland in 2010 (5).

The goal for MenACYW conjugate vaccine is to provide broad protection against IMD caused by serogroups A, C, Y, and W in all age groups including children as young as 6 weeks of age, adolescents, and adults, including those 56 years of age and older. MenACYW conjugate vaccine is an investigational vaccine that is undergoing active clinical investigation. Based on the data generated from previous studies, the immunogenicity profile of the MenACYW conjugate vaccine in different age groups shows that the majority of subjects developed seroprotective levels of antibodies after vaccination. Compared to the currently-licensed in many regions Sanofi Pasteur meningococcal conjugate vaccine, Menactra®, the MenACYW conjugate vaccine is prepared using tetanus toxoid as the carrier protein. Conjugation of polysaccharide antigens to a protein carrier can induce T-cell-dependent immune responses, which are anticipated to give rise to higher antibody titers, longer duration of the immune response, and enhanced immunologic memory that allows for a booster response.

The purpose of MET62 is to describe the immune persistence of the priming dose and describe the immunogenicity and safety of a booster dose of MenACYW conjugate vaccine in children in Finland who had been vaccinated 3 years earlier as toddlers with either MenACYW conjugate vaccine or Nimenrix® as part of the MET54 study.

## 2 Trial Objectives

#### **Immunogenicity**

- 1) To describe the antibody persistence of meningococcal serogroups A, C, Y, and W before a booster dose in children who received either MenACYW conjugate vaccine or Nimenrix® 3 years earlier as toddlers
- 2) To describe the antibody responses to meningococcal serogroups A, C, Y, and W 30 days after a booster dose of MenACYW conjugate vaccine in children who received either MenACYW conjugate vaccine or Nimenrix® 3 years earlier as toddlers
- 3) To describe the antibody responses against tetanus toxoid 30 days after a booster dose of MenACYW conjugate vaccine in children who received either MenACYW conjugate vaccine or Nimenrix® 3 years earlier as toddlers

### Safety

To describe the safety profile of a booster dose of MenACYW conjugate vaccine in children who received either MenACYW conjugate vaccine or Nimenrix® 3 years earlier as toddlers

## 3 Description of the Overall Trial Design and Plan

## 3.1 Trial Design

This is a Phase III, open-label, multi-center study to describe the immune persistence of the priming dose and describe the immunogenicity and safety of a booster dose of MenACYW conjugate vaccine in children in Finland who had been vaccinated 3 years earlier as toddlers with either MenACYW conjugate vaccine or Nimenrix® as part of the MET54 study.

Subjects who were vaccinated 3 years ( $\pm$  45 days) earlier at 12 to 23 months of age in study MET54 were eligible for enrollment in study MET62.

All subjects were to receive a single dose of MenACYW conjugate vaccine on Day (D) 0.

All subjects were to provide blood samples (BL) for immunogenicity assessment at baseline (prevaccination) and at 30 to 44 days after vaccination.

Solicited adverse event (AE) information was to be collected for 7 days after vaccination; unsolicited AE information was to be collected from Visit 1 (D0) to Visit 2 (D30 [+14 days]), and serious adverse event (SAE) information (including adverse events of special interest [AESIs]) was to be collected throughout the study period.

#### 3.2 Trial Plan

A schedule of assessments and study vaccinations is provided in the Table of Study Procedures.

#### Vaccination

All subjects were to receive a single dose of MenACYW conjugate vaccine at Visit 1 (D0).

#### **Blood Sampling**

All subjects were to provide a pre-vaccination blood sample on D0 and a post-vaccination sample at Visit 2 (30 to 44 days after the vaccination at Visit 1).

### Collection of Safety Data

- All subjects were to be observed for 30 minutes after vaccination and any unsolicited systemic AEs occurring during that time were to be recorded as immediate unsolicited systemic AEs in the electronic case report form (CRF).
- The subject's parent / legally acceptable representative was to record information in a diary card (booklet or electronic device [e-diary]) about solicited reactions from D0 to D07 after vaccination and unsolicited AEs from D0 to Visit 2. SAEs were to be reported throughout the duration of the trial.
- In addition, the subject's parent / legally acceptable representative were to be asked to notify the site immediately about potential SAEs at any time during the trial.
- Alerts were to be sent to the e-diary (if applicable) and staff were to contact the subject's parent / legally acceptable representative by telephone on D08 (+2 days) to identify the occurrence of any SAE not yet reported, and to remind them to complete the diary card (booklet or e-diary) up to Visit 2 and to bring it back at Visit 2.
- The completed diary card (booklet or e-diary) was to be reviewed with the subject's parent / legally acceptable representative at Visit 2.

**Note**: The diary card may be either a booklet or an electronic device that contains an application to enter the information (e-diary).

**Table 3.1: Study procedures** 

Phase III Study, 2 Visits, 1 Vaccination, 2 Blood Samples, 1 Telephone Call, 30 Days Duration per Subject

Visit/Contact	Visit 1	Telephone Call 1	Visit 2
Trial timelines (days)	D0	D08	D30
Time windows (days)		+2 days	+14 days
Informed consent	X		
Inclusion/exclusion criteria	X		
Collection of demographic data	X		
Medical history	X		
Physical examination*	X		
Review of temporary contraindications for blood sampling †			X
Allocation of subject number	X		
Blood sampling (BL), 5 mL ‡	BL1		BL2
Vaccination §	X		
Immediate surveillance (30 minutes)	X		
Diary card (booklet or e-diary) provided	X		
Telephone call		X**	
Recording of solicited injection site & systemic reactions	D0 to D07		
Recording of unsolicited AEs	D0 to Visit 2		•
Reporting of SAEs (including AESIs) ††	To be reported throughout the study period		study period
Diary card (booklet or e-diary) reviewed and collected			X
Collection of reportable concomitant medications	X		X
Trial termination record			X

\*Temperature needs to be measured and recorded in source documents.

† Should a subject receive oral or injectable antibiotic therapy within 3 days prior to the second blood draw, the Investigator will postpone that blood draw until it has been 3 days since the subject last received oral or injectable antibiotic therapy. Postponement must still be within the timeframe for blood draw (30 to 44 days after vaccination at D0). If postponement would result in the sample collection falling outside of the 30 to 44 day timeframe, the blood sample should be collected without postponement and it should be documented that the sample was taken less than 3 days after stopping antibiotic treatment.

<sup>‡ Blood sample at Visit 1 will be drawn before administration of vaccine

§ Subjects will receive 1 dose of MenACYW conjugate vaccine

\*\* This call is made 8 to 10 days after the vaccination at Visit 1. If D08 (+2 days) falls on a weekend or holiday, the telephone call may be made on the following business day. During this telephone call, the staff will find out whether the subject experienced any SAE, including AESIs, not yet reported, and will remind the subject's parent / legally acceptable representative to continue using the diary card (booklet or e-diary) up to Visit 2, to bring the diary card (booklet or e-diary) to the study center at Visit 2, and confirm the date and time of Visit 2. Additionally, an alert may be sent to the e-diary (as applicable) to remind the subject's parent / legally acceptable representative to report any SAEs, including AESIs, not yet reported and to continue to use the e-diary up to Visit 2, to bring the e-diary to the study center at Visit 2, and confirm the date and time of Visit 2.

†† AESIs will be collected throughout the trial as SAEs to ensure that the events are communicated to the Sponsor in an expedited manner and followed up until the end of the follow-up period or resolution, as per the assigned causality.

## 4 Endpoints and Assessment Methods

## 4.1 Immunogenicity

See Section 9.1 of the protocol.

## 4.2 Safety

See Section 9.2 of the protocol.

## 4.3 Efficacy

No clinical efficacy data will be obtained in the study.

## 4.4 Derived Endpoints: Calculation Methods

#### **4.4.1** Safety

#### 4.4.1.1 Solicited Reactions

## 4.4.1.1.1 Daily Intensity

All daily records for solicited reactions will be derived into daily intensity according to the following classification: None, Grade 1, Grade 2, Grade 3, or Missing.

For measurable injection site reactions (Erythema/Swelling):

Grade 1: > 0 to < 25 mm

Grade 2:  $\geq$  25 to  $\leq$  50 mm

Grade  $3: \ge 50 \text{ mm}$ 

For measurable systemic reactions (Fever):

Grade 1:  $\geq$  38.0°C to  $\leq$  38.4°C

Grade  $2: \ge 38.5$ °C to  $\le 38.9$ °C

Grade  $3: \ge 39.0$ °C

For the derivation of daily intensities the following sequential steps will be applied:

- 1) Solicited reactions (except Fever/Pyrexia) with an investigator presence recorded as "No" and with all daily records missing then all daily intensities will be derived as None.
- 2) For a temperature partially missing after decimal point, the data will be analyzed replacing "MD" (missing data) by zero. For example, a "39.MD" daily temperature will be considered as "39.0°C" at the time of analysis.

3) For non-measurable solicited reactions, the daily intensities will correspond to the daily records reported in the clinical database. For measurable solicited reactions, the daily measurements reported in the clinical database will be converted based upon the intensity scales defined in the protocol; this assumes that a reaction that is too large to measure (non measurable, "NM") is Grade 3. Note: The maximum intensity on the ongoing period is derived from the record of the maximum intensity/measurement after the end of the solicited period following the rule described above.

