9.2.3 Safety Assessment Methods

At Visit 2, the Investigator or a delegate will ask the subject's parent / legally acceptable representative about any solicited reactions and unsolicited AEs recorded in the diary card (booklet or e-diary), as well as about any other AEs that may have occurred since the previous visit. All relevant data will be transcribed into the CRB according to the instructions provided by the Sponsor.

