## 4.4.1.1.2 Maximum Overall Intensity

Maximum overall intensity is derived from the daily intensities computed as described in Section 4.4.1.1.1 and is calculated as the maximum of the daily intensities over the period considered.

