#### 4.4.1.1.3 Presence

Presence is derived from the maximum overall intensity on the period considered:

- None: No presence
- Grade 1, Grade 2, or Grade 3: Presence
- Missing: Missing presence

Subjects with at least one non-missing presence for a specific endpoint will be included in the analysis. Conversely, those without a non-missing presence will not be included in the analysis of the endpoint.

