## 4.4.1.1.7 Ongoing

Ongoing is derived from the last daily intensity of the solicited period computed as described in Section 4.4.1.1.1 and the maximum intensity on the ongoing period. The investigator's ongoing flag is not used because the measurement would determine the ongoing status of the reaction. Note: The intensity could be considered None (not a reaction) in the analysis despite being considered a reaction by the investigator (e.g., fever > 37.5°C but < 38°C). If the last daily intensity of the solicited period is at least Grade 1 and maximum intensity on the ongoing period is also at least Grade 1, then the reaction is considered ongoing. In any other cases the reaction will not be considered as ongoing.

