## 5.3 Handling of Missing Data and Outliers

#### **5.3.1** Safety

No replacement will be done. In all subject listings, partial and missing data will be clearly indicated as missing.

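### For the six non-fever solicited reactions, a 'No' without daily records counts as reaction-free but a 'Yes' without daily records is excluded, so any such 'Yes' lowers the reported rate

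*SAP*

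**What the plan says.** **Negative answer.** The first derivation step in SAP 4.4.1.1.1 opens with its scope, "Solicited reactions (except Fever/Pyrexia) with an investigator presence recorded as" 'No', and gives the rule: "investigator presence recorded as 'No' and with all daily records missing then all daily intensities will be derived as None". Protocol Tables 9.1 and 9.2 list seven solicited reactions. Fever is excepted, so the step applies to pain, erythema, swelling, headache, malaise and myalgia.

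**Positive answer.** No step addresses it. Step 3 of the same section takes intensity from the daily data alone: "For non-measurable solicited reactions, the daily intensities will correspond to the daily records reported in the clinical database". Erythema and swelling are graded from the daily measurements.

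**Downstream rules.**
- Maximum overall intensity (SAP 4.4.1.1.2) "is calculated as the maximum of the daily intensities over the period considered".
- Presence (SAP 4.4.1.1.3) follows from that maximum, and a Missing maximum gives Missing presence. For such children: "Conversely, those without a non-missing presence will not be included in the analysis of the endpoint".
- The ongoing rule (SAP 4.4.1.1.7) does not bring the child back. It requires the final day of solicited follow-up to carry a graded intensity, so a daily intensity must already exist.
- SAP 5.3.1.4 refers missing solicited intensities back to 4.4.1.1.1 and adds nothing.

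**Data collection.** Protocol 9.2.3 states: "At Visit 2, the Investigator or a delegate will ask the subject's parent / legally acceptable representative about any solicited reactions" recorded in the diary and about other events. Protocol 9.2.1 makes investigator assessment of solicited reactions mandatory, so a presence answer can exist without daily records.

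**The concern.** One field is treated in two ways. When it says there was no reaction, it is accepted in place of the missing daily data. When it says there was a reaction, it is ignored and the child leaves that endpoint. Among children without daily records, inclusion then depends on the outcome being estimated, and the error runs in one direction, towards a more favourable reactogenicity profile.

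Elsewhere the SAP leans the other way. Missing causality counts as related (5.3.1.2), and a reaction too large to measure counts as Grade 3 (4.4.1.1.1).

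The study is descriptive, and solicited reaction rates are a main part of its safety objective. No hypothesis test is affected, but the published percentages and their intervals are.

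Composites could be worse. The SAP does not define a row such as any injection site reaction. A child with 'Yes' for pain and 'No' for erythema and swelling, all without daily records, could be counted there as having had no reaction.

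**Working it through.** The documents give no expected reaction rate, no expected number of children without daily records and no sample size calculation. There is no figure to reproduce, so the check is algebra followed by assumed ranges.

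**Notation, for one non-fever reaction**
- n = children with daily records; x = those among them with the reaction
- a = 'Yes' with no daily records; b = 'No' with no daily records
- N = n + a + b

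**Rates**
- SAP as written: x/(n+b)
- All answers used: (x+a)/(n+a+b)

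**Direction.** Cross-multiplying, (x+a)(n+b) − x(n+a+b) = a(n+b−x). This is positive whenever a > 0 and x < n+b, so the SAP rate is then lower. If a = 0 the two rates are equal. Enumerating 24,570 small cases with a of at least 1 gave none in which the SAP rate was the higher.

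**Size.** Dividing by (n+b)N, the shortfall is (a/N) × (1 − SAP rate). It depends on the number of unrecorded 'Yes' answers and not directly on b. One such child among 188 at a SAP rate near 40% costs about (1/188) × 0.6 = 0.3 points.

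**Illustration at N = 188** (planned total, Protocol synopsis). The fraction without daily records and the true rate are assumptions. The rate among children without records is assumed to equal that in the rest, with counts rounded to whole children.

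| No daily records | True rate | a, b | SAP rate | All answers | Shift (points) |
|---|---|---|---|---|---|
| 2% (4) | 10% | 0, 4 | 18/188 = 9.6% | 18/188 = 9.6% | 0.0 |
| 2% (4) | 40% | 2, 2 | 74/186 = 39.8% | 76/188 = 40.4% | -0.6 |
| 2% (4) | 70% | 3, 1 | 129/185 = 69.7% | 132/188 = 70.2% | -0.5 |
| 5% (9) | 10% | 1, 8 | 18/187 = 9.6% | 19/188 = 10.1% | -0.5 |
| 5% (9) | 40% | 4, 5 | 72/184 = 39.1% | 76/188 = 40.4% | -1.3 |
| 5% (9) | 70% | 6, 3 | 125/182 = 68.7% | 131/188 = 69.7% | -1.0 |
| 10% (19) | 10% | 2, 17 | 17/186 = 9.1% | 19/188 = 10.1% | -1.0 |
| 10% (19) | 40% | 8, 11 | 68/180 = 37.8% | 76/188 = 40.4% | -2.7 |
| 10% (19) | 70% | 13, 6 | 118/175 = 67.4% | 131/188 = 69.7% | -2.3 |

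Formula check at 5% and 40%: (4/188) × (1 − 72/184) = 1.3 points, as in the table.

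**Against sampling error.** The Clopper-Pearson 95% CI at 72/184 is 32.0% to 46.6%, about 7 points either side. With 94 per priming group (equal split assumed), 10% without records and a 40% rate, the SAP gives 34/90 = 37.8% against 38/94 = 40.4%. The shift is again -2.7 points, against a CI of 27.8% to 48.6%, about 10 points either side.

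**The case against.** **The case should be rare.** Protocol 13.2 has staff obtain verbal clarification of missing diary data and transfer it to the case report book. Protocol 11.1 has the investigator interview parents and clarify what is incomplete, and 11.2 adds consistency checks and queries. A 'Yes' with no daily entry is an obvious query. This stands: with no such child there is no bias relative to using all answers, and 2% to 10% without records is an assumption. It does not supply the missing rule. Recall weeks after D07 may yield a yes without day-by-day grades.

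**Step 1 may only decode an entry convention.** If no daily entries are made for a reaction that did not occur, 'No' with no records simply means none. The fever exception fits this, because temperature is measured daily whatever happens. The case report form is not in the documents, so this cannot be settled. It is a good reason to keep step 1, but it does not justify dropping 'Yes'.

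**Stronger readings that a reader might infer, and which the documents do not support:**
- *That every solicited rate is affected.* Step 1 excepts fever. For fever neither answer replaces missing records, so this rule creates no asymmetry.
- *That the child leaves the safety analysis.* Exclusion is endpoint by endpoint under SAP 4.4.1.1.3.
- *That the trigger is a blank diary and the answer is given at Visit 2.* The SAP refers to missing daily records for a reaction. The Visit 2 link is a fair inference from Protocol 9.2.3, but it is not stated.
- *That nothing is learned before Visit 2.* Under Protocol 5.1.4 the D08 call also records health status and reminds parents to complete the D0 to D07 entries.
- *That step 1 contradicts the general safety rule* "No replacement will be done". SAP 5.3.1.4 sends missing solicited intensities to 4.4.1.1.1, which largely makes step 1 a specific exception.

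**Conclusion.** The asymmetry is in the SAP's text, and its direction is certain: for six of the seven solicited reactions the rules can only lower the rate relative to using all answers. Whether they do so depends on at least one child having 'Yes' with no daily records, and the documents do not say how many to expect.

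Under the assumed 2% to 10% without records and true rates of 10% to 70%, the shift is about 0 to -2.7 points, well inside the confidence interval. This would not change the broad safety picture. It is still worth correcting, because the error runs one way, depends on the outcome, and follows from applying the SAP exactly as written.

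**What to change.** In SAP 4.4.1.1.1 and 4.4.1.1.3, add this rule: when investigator presence is 'Yes' and all daily records for that reaction are missing, the child counts as Presence in the 'any' row and in any composite containing that reaction, with intensity, time of onset and number of days of occurrence Missing.

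Keep step 1 for 'No'. Do not seek symmetry by leaving both answers Missing. The rate would become x/n, and if daily entries exist only where a reaction occurred, n would equal x and the rate would go to 100%.

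Report, by reaction and priming group, how many children have 'Yes' and how many have 'No' without daily records, so that readers can see whether the rule mattered.

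**Cost:** one SAP sentence, a grade-missing row in the solicited tables and a short count table. No new data are needed. The downside is that a few reactions are counted without a grade, so the graded rows will not add up to the 'any' row unless the grade-missing row is shown.
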